2.5. Description and justification of the mode of administration, dose, and dosage regimen

According to the legal and regulatory basis, the study will use samples of the investigational product and the comparator provided by the Sponsor.

The study will include evaluation of the efficacy and safety of Polyoxidonium®, lyophilizate for solution for injections and topical application, 6 mg (NPO Petrovax Pharm LLC, Russia) in patients with COVID-19.

In this study, the investigational product will be administered to hospitalized adult patients with COVID-19:

All patients will be administered Polyoxidonium®, lyophilizate for solution for injections and topical application, 6 mg (NPO Petrovax Pharm LLC, Russia) in dose of 12 mg after reconstitution once daily intravenously (IV) for 3 days, then every other day intramuscularly (IM) on days 5–17 (the total treatment course is 10 injections).

Polyoxidonium® was shown to be effective in the treatment of infectious diseases, in particular, acute respiratory infections in the previous clinical trials and clinical practice [Pružinec P., Chirun N., Sveikata A., 2018; Harit S.M. et al., 2017]. Polyoxidonium® as an adjunct to traditional therapy in both children and adult patients leads to the normalization of

T-cell parameters and the phagocytic activity of neutrophils in the treatment of infectious diseases of various etiology. Polyoxidonium® reduces the duration of the inflammatory process and prevents relapse. The highest prophylactic effectiveness of the Polyoxidonium® was with the dose of 24 mg/day [Kharit S.M., Galustyan A.N., 2017; Skachkov M.V., 2007]. Based on the available efficacy data, Polyoxidonium® should be considered for evaluation in clinical studies as a treatment of COVID-19.

According to the Instructions for human use of Polyoxidonium®, lyophilizate for solution for injections and topical application, 6 mg (NPO Petrovax Pharm LLC, Russia), the drug is administered parenterally in doses of 6-12 mg once a day, every other day, or 1-2 times a week, depending on the diagnosis and severity of the disease. In patients with acute viral and bacterial infections of ENT organs and upper respiratory tract, the dose of 6 mg is administered every day for 3 days, then every other day (10 injections in total). In addition, the dose of 12 mg is allowed for use in complicated diseases, for example, acute and chronic allergic diseases complicated by bacterial, viral, or fungal infection [IHU].

The drug was administered parenterally in the dose of 12 mg in patients with breast cancer and skin melanoma in clinical trials [Monakhov A.S. et al., 2010; Shamilov F.A. et al., 2013].

Based on the clinical studies and the post-marketing experience, Polyoxidonium® has a favourable safety profile. The general tolerability of the drug was evaluated as follows in a large post-marketing study by the investigators and patients: 75.3% of patients and 79.7% of doctors rated the tolerance of the oral dosage form as 'very good', 21.1% of patients and 19.3% of doctors rated the tolerance as 'good'. Treatment of acute respiratory infections was also investigated in the clinical studies in the paediatric population at various dosages. No statistically significant difference ($p > 0.05$) was found in the incidence of AE between the main group and the control group [Shirokova I., 2017; Kharit S.M., Galustyan A.N., 2017].

Thus, taking into account the severity of the disease, pronounced symptoms, in particular, severe acute respiratory syndrome, it is planned to evaluate the effectiveness of IP in the maximum dose and in the dosage regimen for acute viral infections of the respiratory tract. Given the favourable safety profile of IP, increasing the dose per treatment course is not likely to increase the risks for patients. It is expected that this approach will achieve the most profound therapeutic effect with a low risk of adverse events.

The risk to subjects can be minimized by excluding those with significant underlying severe renal disease, and appropriate monitoring during the study.

To date, there is no evidence of the effectiveness of any drug against 2019-nCoV. The disease should be treated according to the existing international and national recommendations in force at the time of the study. Patients infected with 2019-nCoV should receive supportive symptomatic therapy. The comorbid conditions and complications should be treated in accordance with clinical guidelines, standards of medical care for these diseases, conditions¹, and complications in force in the relevant country at the time of the planned clinical trial.

If the concomitant condition is not an inclusion/exclusion criterion, the treatment of such condition within this protocol should follow the standard of care. The concomitant medications should not be prohibited by this protocol.

The enrolled patients will receive full treatment in accordance with the standards of supportive treatment.

2.6. Statement on quality of the study

The observational study will be conducted according to the current version of the study protocol and routine practice of the health care institution. The Protocol with any amendments as well as the Patient Information Leaflet and the Informed Consent Form should be approved by the local ethics committee and should not contradict the routine clinical practice.

This is a non-interventional study protocol. The study will be conducted in accordance with the principles of the Helsinki Declaration of the WMA (adopted at the 18th Assembly of the WMA in Helsinki in June 1964; the latest edition was approved at the 64th Assembly in Fortaleza in October 2013) and is regulated by the current legislation of the EAEU and the Russian Federation. The definition of ‘non-interventional study’ is given in Good Clinical Practice of the Eurasian Economic Union that was approved by the Eurasian Economic Commission Council Resolution dated November 3, 2016, No. 79. Features of a non-interventional study are presented in the Decision of the Eurasian Economic Commission No. 87 dated November 3, 2016 ‘On the Approval of Good Clinical Practice of Pharmacovigilance of the Eurasian Economic Union’. According to this document, a non-interventional study should meet the following conditions:

- a drug is prescribed in accordance with the summary of product characteristics,
- the decision to prescribe a specific treatment to the patient is not made in compliance with the routine clinical practice, rather than the study protocol, and the prescription is clearly separated from the decision to include the patient in the study,
- no additional diagnostic or control procedures are applied to patients, and epidemiological methods are used to analyse the collected data.

Non-interventional studies are defined by the methodological approach and not by scientific objectives. Recommendations regarding non-interventional studies are given in the Code of Practice for the Association of International Pharmaceutical Manufacturers (2015), as well as in the Good Clinical Practice of the Eurasian Economic Union.

The personal data will be collected and processed during this study in accordance with applicable local legislation (in particular, in accordance with Federal Law No. 152-FZ ‘On Personal Data’ dated July 27, 2006 in Russia).

2.7. Study Population

The patient inclusion criteria were validated scientifically. The main inclusion criterion is a confirmed diagnosis of COVID-19.

Standard case of the novel 2019-nCoV coronavirus infection [Temporary guidelines, 2020]

Suspected 2019-nCoV infection:

- clinical manifestations of an acute respiratory infection, bronchitis, pneumonia in combination with the following epidemiological history:
- a visit to the epidemiologically unfavourable for 2019-nCoV countries and regions (mainly Wuhan, China) in the last 14 days before the onset of symptoms,
- close contacts over the past 14 days with persons under surveillance for the novel coronavirus 2019-nCoV infection, who subsequently became ill,
- close contacts over the past 14 days with people who had their 2019-nCoV diagnosis confirmed by laboratory testing.

Probable 2019-nCoV infection:

- clinical manifestations of severe pneumonia, ARDS, sepsis in combination with relevant epidemiological history (see above).

Confirmed case of 2019-nCoV1 infection¹:

¹ Temporary guidelines. Prevention, diagnosis, and treatment of the novel coronavirus infection (2019-nCoV). Version 2 (02/03/2020). Electronic source. Free access: <https://static-1.rosminzdrav.ru/system/attachments/attaches/000/049/329/original/%D0%92%D1%80%D0%B5%D0%BC%D>

1. Clinical manifestations of an acute respiratory infection, bronchitis, pneumonia in combination with the epidemiological history.
2. Positive laboratory test results for 2019-nCoV RNA by polymerase chain reaction (PCR).

3. AIM AND OBJECTIVES OF THE STUDY

3.1. Study Aim

To evaluate safety and efficacy of Polyoxidonium® (azoximer bromide) as an addition to complex treatment of hospitalized patients with COVID-19.

3.2. Study Objectives

1. To evaluate clinical efficacy of Polyoxidonium®, lyophilizate for solution for injections and topical application, 6 mg (NPO Petrovax Pharm LLC, Russia) in hospitalized adult patients with COVID-19.
2. To evaluate safety of Polyoxidonium®, lyophilizate for solution for injections and topical application, 6 mg (NPO Petrovax Pharm LLC, Russia) in hospitalized adult patients with COVID-19.

4. STUDY DESIGN

4.1. Primary and Secondary Outcomes

According to the aim and objectives of this study, safety and efficacy of Polyoxidonium®, lyophilizate for solution for injections and topical application, 6 mg (NPO Petrovax Pharm LLC, Russia) will be evaluated in hospitalized patients with coronavirus disease (COVID-19).

Efficacy outcomes

Primary efficacy outcome

Subject clinical status using the WHO 7-point ordinal scale on day 15 as compared to baseline.

1. Not hospitalized, no limitations on activities.
2. Not hospitalized, limitation on activities.
3. Hospitalized, not requiring supplemental oxygen.
4. Hospitalized, requiring supplemental oxygen.
5. Hospitalized, on non-invasive ventilation or high flow oxygen devices.
6. Hospitalized, on invasive mechanical ventilation or ECMO.
7. Death.

Secondary efficacy outcomes

Clinical severity assessed by scales

1. Subject clinical status using the WHO 7-point ordinal scale

- Time to improvement of each parameter of the primary scale from admission.

- Subject clinical status at days 3, 5, 8, 11, and 29.
 - Average change in the clinical status at days 3, 5, 8, 11, 15, and 29 as compared to baseline.
2. *The NEWS Score (National Early Warning Score) describes the vital signs (pulse rate, breathing rate, temperature, blood pressure etc.) and its deviation from the reference ranges):* is evaluated daily and on day 15.
- The time to discharge or to a NEWS of ≤ 2 and maintained for 24 hours, whichever occurs first.
 - Change from baseline to days 3, 5, 8, 11, 15, and 29 in NEWS.
3. *Oxygenation, including mechanical ventilation:*
- Change (day by day) in the need for oxygenation in the first 28 days (up to day 29).
4. *Hospitalization*
- Duration of hospitalization (days).
5. *Mortality (date, cause)*
- 28-day mortality.
6. *SOFA scale (evaluation of organ failure associated with sepsis):* is evaluated daily and on day 15.
- Change from baseline to days 3, 5, 8, 11, 15, and 29 in SOFA.

Safety outcomes

Safety outcomes

- Cumulative incidence of serious adverse events/reactions (SAEs, SARs)
- Cumulative incidence of adverse events/reaction (AEs, ARs)
- Permanent or temporary discontinuation of infusions/injections (by any cause)
- Clinically significant changes in the levels of leukocytes, haemoglobin, platelets, creatinine, glucose, total bilirubin, ALT, AST, CRP, and other parameters.

The safety of the investigational product will be evaluated based on statistical analysis of the specified parameters.

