Open multi-centre observational study of efficacy and safety of a medicinal

	
product.
 
The clinical efficacy will be assessed by changes in the patient's clinical status, duration of hospitalization, oxygenation/mechanical ventilation. The clinical examination will include clinical, laboratory, and instrumental investigations according to the current guidelines on treatment of COVID-19 in the Russian Federation.

POPULATION	Hospitalized patients of 18 years and older with confirmed COVID-19.
SAMPLE SIZE	At least 50 patients
TREATMENT ALLOCATION	All study subjects will receive treatment with Polyoxidonium, lyophilizate, 12 mg, in addition to the standard treatment
DIAGNOSIS	Verified COVID-19

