5. SCREENING AND WITHDRAWAL OF THE SUBJECTS

5.1. Inclusion criteria

1. The patient is already receiving, or the patient have been prescribed therapy with Polyoxidonium® in accordance with the approved labelling in combination with COVID-19 therapy recommended by the Ministry of Health of the Russian Federation.
2. Verified diagnosis: COVID-19.
3. Severity of the disease at hospitalization:
 - severe disease: requiring mechanical ventilation or oxygen, a $SpO_2 \leq 94\%$ on room air or tachypnoea (respiratory rate ≥ 24 breaths/min).
 - mild-moderate disease: $SpO_2 \geq 94\%$ and respiratory rate ≤ 24 breaths/min without supplemental oxygen.
4. Patients who signed the informed consent.
5. Understands and agrees to comply with planned study procedures.
6. Age ≥ 18 years old at the enrolment.
7. Has laboratory-confirmed SARS-CoV-2 infection as determined by PCR, or other commercial or public health assay in any specimen prior to the enrolment.

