6.2. Description of the visits

A comprehensive description of visits (by days) is provided in Appendix 1. All procedures described below should be carried out as part of the routine practice of the health care institution.

Preliminary evaluation of the inclusion/exclusion criteria

(Before the study initiation)

Full list of the procedures is provided in Appendix 1.

- Signing of informed consent.
- Confirmation of the positive test for SARS-CoV-2¹.
- Collection of patient history, demographics, and anthropometric data.
- Collection of information about previous/concomitant treatments.
- Physical examination (including lung auscultation).
- Evaluation of chest X-ray or CT scans².
- Laboratory test³: haematology, biochemistry, urinalysis.
- Oxygen saturation (SpO₂).
- Evaluation of the eligibility.

Treatment period

Day 1 - enrolment, initiation of the treatment

Full list of the procedures is provided in Appendix 1.

- Evaluation of measures of clinical support.
- Assessment of the clinical status according to the 7-point ordinal scale.
- Assessment of the clinical status according to the NEWS scale and SOFA scale.
- Oropharyngeal/nasal (OP/N) sample.
- Haematology (only if this test was not performed at the screening).
- Blood chemistry (only if this test was not performed at the screening).
- Urinalysis (only if this test was not performed at the screening).
- Administration of the investigational product
- Physical examination (including lung auscultation).
- Collection of the efficacy data (oxygenation, mechanical ventilation, prolongation of

¹ Data obtained not later than 48 hours before signing the informed consent may be used.

² Recent chest X-ray/CT scans can be used, if the scans were obtained after the coronavirus disease (COVID-19) was diagnosed.

³ If the patient has results of laboratory tests that were performed within 48 before the enrolment, these results can be used to assess the clinical status and eligibility. These data can be used only if they are complete and include all parameters specified in the Protocol. Repeated laboratory tests on Visit 0 are not required in this case.

hospitalization).

- Recording of AEs.

Days 2...18

Full list of the procedures is provided in Appendix 1.

The visits are performed in the in-patient settings. If the patient is discharged before Day 17, the procedures will be performed at the outpatient visits to the clinic.

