6.3.5. Laboratory tests

The schedule of laboratory tests is included in description of the study parts and in the schedule of the study procedures.

List of the evaluated laboratory parameters

¹ Temporary guidelines. Prevention, diagnosis, and treatment of the novel coronavirus infection (2019-nCoV). Version 2 (02/03/2020). Electronic source with free access: <https://static-i.rosminzdrav.ru/system/attachments/attaches/000/049/329/original/%D0%92%D1%80%D0%B5%D0%BC%D0%B5%D0%BD%D0%BD%D1%8B%D0%B5%D0%9C%D0%A0%2019-nCov%2003.02.2020%28%D0%B2%D0%B5%D1%80%D1%81%D0%B8%D1%8F%29%29%20final.pdf?1580748451>.
Access date: March 16, 2020.

Haematology

Red blood cells, haematocrit, white blood cells, platelets, neutrophils, eosinophils, basophils, monocytes, lymphocytes

The volume of the blood sample is approximately 5 mL.

Blood chemistry

Urea, creatinine, Na⁺, K⁺, bilirubin, glucose, ALT, AST, albumin, pH, bicarbonates, lactate, coagulogram with prothrombin time, coagulogram with international normalized ratio and activated partial thromboplastin time, CRP. The blood sample volume is approximately 5 mL.

If indicated: PaO₂, FiO₂, PaCO₂

Urinalysis

According to routine practice of the centre.

Test for SARS-CoV-2

The test is performed at the screening to assess the eligibility. Data obtained not later than 48 hours before signing the informed consent may be used.

Oropharyngeal/nasal (OP/N) sample

Oropharyngeal/nasal samples will be taken in accordance with the routine practice of the health care institution.

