9. STATISTICS

9.1. Statistical analysis

Analysis of the primary endpoint

The primary efficacy outcome for the first part of the study is ‘Clinical status of the patient (according to 7-point ordinal scale) on day 15 as compared to baseline’.

Analysis of the secondary endpoints

The interval (quantitative) data will be described with arithmetic mean, standard deviation, median, lower quartile (25%) and higher quartile (75%), minimum, maximum, coefficient of variation, and 95% confidence interval for the mean. The categorical (qualitative) data will be described with incidences, percentage, or proportions, and 95% confidence interval for percentage or proportions.

The time to event data will be processed via survival analysis with the use of Kaplan-Meier curves and 95% confidence intervals.

The following standard parametric tests are planned for comparison of quantitative data with normal distribution: Student t-test, analysis of variance (ANOVA) for repeated measurements.

The following standard non-parametric tests are planned for comparison of quantitative data with distribution other than normal: Mann-Whitney U-test, Wilcoxon T-test, Friedman test.

Shapiro-Wilk test will be used to test normality of the distribution.

The incidences will be compared with Pearson’s χ^2 -test or Fischer’s exact test.

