16. APPENDICES

SCHEDULE OF ASSESSMENTS

Table 1. Study plan
(ALL THESE PROCEDURES SHOULD BE CARRIED OUT IN THE FRAMEWORK OF ROUTINE PRACTICE OF THE HEALTH CARE INSTITUTIONS)

Procedure / days	Study according to the Protocol No. COVID dated March 30, 2020				
	Day 1	Daily (up to discharge ^{***})	Day 3, 5, 7, 11	Day 15±1	Day 29±3 or any other last day ^{****} of the study
Enrolment criteria	X				
Withdrawal criteria		X	X	X	X
Informed consent, enrolment	X				
Polyoxidonium	10 doses: days 1, 2, 3, 5, 7, 9, 11, 13, 15, 17				
History	X				
Clinical signs and symptoms, physical examination¹	X	X	X	X	X
Nasopharyngeal and/or oropharyngeal smear	X		X	X	X
Haematology²	X**		X	X	X
Blood chemistry³	X**		X	X	X
CRP	X**		X	X	X
Urinalysis⁴	X**		X	X	X
Bacteriological inoculation of sputum	If necessary				
Chest X-ray/ CT*	If indicated				
ECG*	If indicated				
SpO₂⁵	X	X	X	X	X
Evaluation of need for oxygenation, including mechanical ventilation	X	X	X	X	X
Assessment of the treatment efficacy⁶	X	X	X	X	X
Assessment of safety	X	X	X	X	X
NEWS Score	X	X	X	X	X
SOFA Score	X	X	X	X	X
Clinical status by WHO scale	At admission	X	X	X	X

Notes to Table 1

*- including at admission, before enrolment

** - results of the previous laboratory investigations within 48 hours before enrolment can be used

*** - visits to the clinic are preferred after discharge, but the quarantine or other reasonable factors can limit this opportunity. The visits could be performed in a form of phone call or with other remote communication technologies. Some data will not be collected by obvious reasons.

**** - in case of the patient withdrawal (see the withdrawal criteria)

1 – Clinical signs and symptoms

Weakness, fatigue, cough, shortness of breath, stuffiness in the chest, myalgia, headaches, haemoptysis, palpitations, nasopharyngeal symptoms, diarrhoea, nausea, vomiting; physical

examination: heart rate, blood pressure, respiratory rate, body temperature

2 – Haematology

Red blood cells, haematocrit, white blood cells, platelets, neutrophils, eosinophils, basophils, monocytes, lymphocytes

3 - Blood chemistry

Urea, creatinine, Na⁺, K⁺, bilirubin, glucose, ALT, AST, albumin, pH, bicarbonates, lactate, coagulogram with prothrombin time, coagulogram with international normalized ratio and activated partial thromboplastin time, CRP

If indicated: PaO₂, FiO₂, PaCO₂

4 – Urinalysis

According to routine practice of the centre

5 - SpO₂

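### Time to improvement is referred to hospital admission while Day 1 is enrolment, with no limit on the gap, so the planned Kaplan-Meier estimate absorbs the course before enrolment

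*Combined protocol and SAP*

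**What the plan says.** The synopsis, section 4.1 and section 7.1 all list, under the 7-point scale, "Time to improvement of each parameter of the primary scale from admission". Section 6.2 defines study time differently: "Day 1 - enrolment, initiation of the treatment". The visit-based endpoints (days 3 to 29), the dosing days and the follow-up period all count from Day 1.

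The plan treats admission and enrolment as separate events. The note to the chest imaging and ECG rows of Table 1 (section 16) reads "including at admission, before enrolment", and the table of non-interventional criteria in section 4.2 places the prescription before inclusion.

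The population in the synopsis is "Hospitalized patients of 18 years and older with confirmed COVID-19". Section 5.1 grades "Severity of the disease at hospitalization", not at enrolment, and its first criterion is "The patient is already receiving, or the patient have been prescribed therapy with Polyoxidonium® in accordance with the approved labelling". Sections 5.1 and 5.2 set no maximum time from admission, or from first dose, to enrolment. The windows that do exist concern the age of test results: for the SARS-CoV-2 test, "Data obtained not later than 48 hours before signing the informed consent may be used" (section 6.3.5), with a similar 48-hour window for laboratory results.

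For the analysis, section 9.1 states "The time to event data will be processed via survival analysis with the use of Kaplan-Meier curves", and section 9.7.2.2 repeats it. Neither section mentions delayed entry. Improvement is not defined: the size of the step and whether it must be sustained are left open.

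**The concern.** Two things can go wrong when admission is the origin or reference and enrolment comes later.

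First, a patient who is discharged or dies before consent is not enrolled. Every enrolled patient therefore brings an interval in which discharge and death were impossible by selection. Ordinary Kaplan-Meier from admission treats that interval as time at risk.

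Second, a patient who improves in hospital before Day 1, for example from score 4 to score 3, can still be enrolled. Judged against the admission score, that improvement counts as an efficacy event although it came before the study's Day 1.

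The curve would then partly reflect how quickly each centre enrols. The study has one group, so the absolute estimate is all the reader gets, and no comparison is available in which the distortion might cancel.

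**Working it through.** **No figure to reproduce.** The plan gives no expected delay, no median time to improvement and no derivation of the sample size of at least 50. Everything below is illustration on assumed values.

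**Which mechanism applies to whom.** On the 7-point scale, a patient at score 3 can improve only to 2 or 1, and both mean out of hospital. For such a patient any improvement before consent prevents enrolment. A patient at 4, 5 or 6 can improve by one step and remain in hospital, so enrolment is still possible. Both mechanisms can operate, because section 5.1 admits both mild-moderate and severe disease.

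**Assumptions.** Let *T* be time from admission to improvement, Weibull with median *m* and shape *k*, so S(t) = 2^(−(t/m)^k). Shape *k* = 1 is a constant hazard; *k* = 1.5 is a rising one. *D* is the delay from admission to Day 1. Assumed ranges: *m* = 7, 10 or 14 days; *D* = 0 to 7 days.

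**Case A: patients who improve before Day 1 are not enrolled.** The median among those enrolled solves S(t) = S(D)/2, which gives t = (m^k + D^k)^(1/k). For *m* = 10:

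- *k* = 1: t = 10 + D. For D = 0, 1, 3, 5, 7 the median from admission is 10, 11, 13, 15, 17 days. From Day 1 it is 10 each time.
- *k* = 1.5, D = 3: (31.62 + 5.20)^(2/3) = 11.1 days from admission; 11.1 − 3 = 8.1 from Day 1.
- *k* = 1.5, D = 7: (31.62 + 18.52)^(2/3) = 13.6 days from admission; 13.6 − 7 = 6.6 from Day 1.

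A simulation with 60,000 patients per scenario and censoring 28 days after Day 1 agrees with these to about 0.1 day. It also covered a delay spread evenly over 0 to 7 days, with *m* = 10:

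| Shape | From admission, ordinary Kaplan-Meier | From admission, delayed entry | From Day 1 |
|---|---|---|---|
| 1.0 | 13.3 | 10.1 | 10.0 |
| 1.5 | 11.4 | 10.0 | 8.0 |

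Delayed entry recovers the true 10 days in both rows. The Day 1 figure answers a different question, time from enrolment, and under a rising hazard it too varies with the delay.

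**Case B: patients who improve before Day 1 are all enrolled and counted.** The median from admission stays at *m*, but a share 1 − 2^(−(D/m)^k) improves before Day 1:

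- *m* = 10, D = 3: 1 − 2^(−0.3) = 18.8% for *k* = 1; 1 − 2^(−0.164) = 10.8% for *k* = 1.5.
- D = 3, over all assumed *m* and *k*: 6.6% (*m* = 14, *k* = 1.5) to 25.7% (*m* = 7, *k* = 1), or 3.3 to 12.9 of 50 patients.
- D = 7: 21.7% to 50.0%, or 10.9 to 25 of 50 patients.

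**Deaths.** Patients who die before consent would never have improved. Leaving them out pushes the estimate towards more improvement, against the lengthening in case A. The net direction is therefore not fixed. With D = 0 none of these effects arises.

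**The case against.** The endpoint wording can be read as improvement relative to the admission score, with no statement about the clock. Table 1 favours that reading: under Day 1, its WHO-scale row gives admission as the time of assessment, although section 6.2 lists a scale assessment on Day 1. The ambiguity is real. On this reading, however, the clock start is simply missing, and an improvement between admission and Day 1 still counts.

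The plan schedules no 7-point score between admission and Day 1, so an exact event date in that interval would need the hospital chart. That stands. A Day 1 score better than the admission score would nevertheless show that the patient had already improved.

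A reader might infer that the whole interval before enrolment is untreated. The documents do not support this: the first criterion in section 5.1 admits patients already on the drug, so for them part of the interval may be treated time. That criterion also conflicts with section 6.2, which starts treatment on Day 1, and the two passages must be reconciled.

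A reader might also infer that a Day 1 clock is immune to enrolment speed. That holds only for a constant hazard; with shape 1.5 the Day 1 median falls from 8.1 to 6.6 days as the delay grows from 3 to 7.

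Finally, this is one secondary outcome in a single-group study, and neither clock would let the curve attribute improvement to the product. That stands and limits the weight of the point.

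**Conclusion.** The point holds in limited form. The endpoint takes admission as its origin or reference, Day 1 is enrolment, nothing limits the gap, and the planned Kaplan-Meier analysis has no delayed entry. As written, the estimate includes guaranteed event-free time, improvements before Day 1, or both.

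The size cannot be computed from the documents. Under the assumptions above, a 3-day delay with a true median of 10 days adds 1.1 to 3 days to the median if improvers are not enrolled. It adds nothing if they all are, but then 10.8% to 18.8% of patients improve before Day 1.

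A reader might infer that the median is overstated by several days. That requires improvement to prevent enrolment, which is not so for a step from 4 to 3 in hospital. Nor is this a between-group bias, since there is no second group. It is an avoidable distortion of a descriptive secondary estimate, and worth correcting because correction is cheap.

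**What to change.** - In the synopsis, 4.1 and 7.1, start the clock at Day 1, measure improvement against a WHO score taken on Day 1, and count only later improvements. Define improvement: how many steps, and whether it must be sustained.
- In Table 1, change the WHO-scale entry under Day 1 from admission to a Day 1 assessment, in line with section 6.2. Otherwise the table contradicts the new reference score.
- State the same origin for time to discharge or NEWS ≤2, which currently has none.
- Record the dates of admission, first dose and enrolment, and report the distribution of the delay.
- Add a sensitivity analysis that excludes, or shows separately, patients who received the drug before enrolment.
- If admission is kept as the origin, use Kaplan-Meier with delayed entry at enrolment, restricted to patients who had not yet improved at entry.

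The cost is wording in three places, one table entry, three dates and a little more analysis work, with no extra patients or visits. The downside is that improvements before Day 1 in patients already on the drug do not count in the main curve.
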